Untoward, Adverse Events Associated with CHG. While chlorhexidine has become a widely utilized antiseptic, it is not used without risk. With the assistance of [name] MLIS, the hospital librarian, an extensive literature search for untoward or adverse events associated with CHG revealed a number of concerning documents citing problems including mild skin irritation, Allergic Contact Dermatitis (ACD) and anaphylaxis. Most notably though, the more serious reactions were related from direct exposure to multiple products containing CHG and CHG impregnated devices (Khoo & Oziemski, 2010; Kutzscher, 2012), or direct contact between the CHG product and the mucous membranes of the individual. (Khan et al, 2011). In general, there were no serious events associated with CHG bathing cloths, with most reports citing only mild skin reactions. (Vernon et al, 2006; Bleasdale et al, 2007; Darmstadt et al, 2007; Sankar et al, 2009; Milstone et al, 2013).

Purpose Statement

Daily CHG baths are a proven method for preventing HAIs in patients greater than 2 months of age and older. However, CHG has been shown to be absorbed through the skin of premature and term infants and safe CHG bloodstream levels are not known. Thus the use of CHG in infants less than 2 months of age remains controversial.

Like many ICUs across the nation, the ICUs at Boston Children's Hospital have been using CHG on a limited basis for CVC insertion and CVC dressing changes on all babies greater than 28 weeks PMA for almost 2 years. During this time, we have not observed any untoward effects to the skin's surface. Though despite our best efforts, HAIs remain problematic, and thus we remain reluctant to expand the use to daily CHG baths without a better understanding of the risks and benefits. In effort to secure the benefit of CHG baths while minimizing risk of bloodstream absorption, our study team has elected to investigate the safety of twice-weekly 2% CHG baths in a sample of newborns (36 weeks PMA or older, less than 2 months of age or 48 weeks PMA, with a CVC). This study will examine the safety of twice weekly CHG baths and provide data to support a larger study that will examine efficacy. The research questions to be answered by this study are as follows:

Research Question 1:

Are twice weekly CHG baths safe for use in a sample of infants 36 weeks PMA or older, and less than 2 months of age (48 weeks PMA) with a CVC?

Hypothesis 1:

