CHG will be safe for use in a sample of infants 36 weeks PMA or older, and less than 2 months of age (48 weeks PMA) with a CVC as evidenced by an adverse event rate less than 10%.

Research Question 2:

Does twice weekly CHG baths lead to rising (cumulative) CHG blood levels, liver function tests (LFTs -AST/ALT) and Serum Creatinine over time in a sample of infants 36 weeks PMA or older, and less than 2 months of age (48 weeks PMA) with a CVC?

Hypothesis 2:

Twice weekly CHG baths do not lead to rising (cumulative) CHG blood levels, LFTs (AST/ALT)

and Serum Creatinine over time in a sample of infants 36 weeks PMA or older, and less than 2 months of age (48 weeks PMA) with a CVC.

Methods

Study Design: A pilot study using a single arm trial design.

Study Sample: Our convenience sample will include 50 infants. Infants admitted to the NICU or pediatric CICU will be eligible to participate.

Inclusion criteria.

- Greater than/equal to 36 weeks PMA (gestational age + chronological age)
- Less than/equal to 48 weeks PMA (gestational age + chronological age)
- Greater than/equal to 3 days of age
- Existing or soon to be placed, peripheral or surgical CVC
- Permission to participate in trial by attending physician
- Parent or legal guardian informed consent to participate in the trial

Exclusion criteria.

- Infant with a large open lesion or severe skin condition (i.e., Myelomeningocele, Gastroschisis, lymphatic malformation, open chest, ostomies and/or mucus fistulas or Icthyosis)
- Infants with active seizure disorders
- Infants with Hypoxic Ischemic Encephalopathy
- Infants with severe multi-system organ failure or Liver failure as defined by documentation of abnormal liver function tests: alanine aminotransferase (ALT) and aspartate aminotransferase (AST) Gamma-glutamyltransferase (GGT) and L-lactate dehydrogenase (LD).
- HCT \leq 28%: Respiratory support (mechanical ventilation, continuous positive airway pressure or high flow nasal cannula with FiO₂ > 25% Oxygen by nasal cannula > 1 liter/min) or HCT \leq 25%: No respiratory support.
- Infant with renal impairment as defined by: documented serum Creatinine greater than 0.7, renal disorders (renal agenesis, polycystic kidney disease, dysplastic kidneys, acute renal injury).
- Infants deemed clinically unstable by their physician such as patients that are extremely fragile and wouldn't tolerate the stimulation of the bathing process or those infants being considered for withdrawal of care.

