Setting: Boston Children's Hospital (BCH), a non-profit, Magnet® certified pediatric teaching and research hospital, is a 395 bed hospital that admits over 17,000 patients per year. This study will be conducted in our 24-bed Level IV NICU and a 29 bed pediatric CICU; both serve as tertiary care referral centers for critically ill infants.

During 2012, BCH NICU admitted 616 critically ill infants; 463 infants were admitted to the medical service and 153 were admitted to the surgical service. (NICU, 2012) The average length of stay was 12.7 days with a range of 2- 273 days. The BCH NICU admits infants up to 64 weeks PMA (6 months), though more than 98.7% of infants admitted during 2012 were less than 48 weeks PMA (2 months), and 86.5% were admitted at less than 44 weeks PMA (1 month). The NICU patient population consists of infants with complex medical and surgical conditions, with a vast range of diagnoses including, but not limited to Prematurity (41.4%), Respiratory distress-multiple causes (17%), rule out seizures (5%) and Patent Ductus Arteriosus (2%). In 2012, the NICU maintained an average of 3187 central lines days

though this number does not reflect the presence of multiple simultaneous central lines on any given patient.

In 2012, BCH pediatric CICU admitted 1364 critically ill children with 377 admissions being less than 2 months of age (48 weeks PMA; CICU 2012). The average LOS for this age group was between 9-15 days. The pediatric CICU maintained 6,917 CVCs, and nearly 100% of infants requiring surgical correction for their cardiac anomaly have at least 1 CVC placed.

Study Procedures:

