- Properly labeled bath cloths with the additional label will be delivered by ISD Pharmacy staff and placed directly into the locked study cloth warmer in the CICU. (The cloth warmer will be housed in a locked unit that requires ID card for entry and a locked warmer that requires a code to enter, and only study team members will have access to the code).
- To ensure all bath cloths are warmed prior to use, the PI or her designee will document the warmer temperature on the CHG Warmer Temperature Log (Appendix A) daily. One CHG Warmer Temperature log will be kept with each warmer in the NICU and the CICU.
 - The warmer temperature of 100°F (37.8°C) is in compliance with the package label and is compliant with the FDA's recommendation. The PI and one alternate (co-investigator) will have the passcode key that is required to adjust the set temperature. The Sage warmer is also equipped with status indicators for heating each individual package. A red light blinks to indicate when the CHG Cloths are to be disposed (after 84 hours in the warmer).

- Nurses performing the CHG bath intervention in the NICU and pediatric CICU will sign and date the extra label bearing the unique identifying number and place it on the CHG Bath Data Collection Tool (Appendix B). The nurses will also sign and date the label of the product package.
- After use, the used/soiled bath cloths will be disposed of in standard waste receptacles, and the empty packaging will be placed in a sealed container in a locked cabinet located in the Annex before return to IDS pharmacy.

CHG bath training. Experienced and trained NICU and pediatric CICU RNs who are familiar with the ICU equipment will administer the study intervention (CHG baths). The RNs will receive training to administer baths at a maximum of 2 times a week (Monday and Thursday). The RNs will wash around any tubes, drains and wires that need to stay in place during the bathing procedure. If needed, wires and leads can be changed at this time to allow thorough cleansing of all intact skin surfaces. The bathing procedure is as follows:

- Assess whole body for any skin lesions before bathing
- Apply clean diaper to the study subject and fold the diaper down to the abdominal crease in the front and the level of the iliac crest in the back
- Perform bath using pre-warmed 2% CHG impregnated rinse-free cloths by Sage Inc. Each package is for individual use only
- Cleanse body downward, starting at the neck

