- Rub area to be cleansed with a back and forth motion
- Use 1 cloth for neck, arms, and legs (stopping at ankles to prevent wiping of feet/heels)
- Use second cloth for torso and back

CHG Bath Intervention. Subjects whose parents consent for this study will receive a CHG bath twice weekly. The CHG baths will be performed by 1 of 5 trained study nurses on each unit to ensure a standard bathing technique. Baths will be performed every Monday and Thursday during the day shift, for up to 12 weeks post enrollment or until the CVC is removed or the patient is discharged. Nurses will use pre-warmed 2% CHG impregnated non-sterile cloths from Sage Products Inc. CHG bath cloths will be pre-warmed to 100°F (37.8°C) in the warmers provided by Sage Products Inc. Baths will entail cleaning the infants with 2 CHG bathing cloths (1 package) beginning at the neck, working down the body toward the feet. Nurses will be instructed not to use the CHG cloths on the face, scalp, or over open body orifices or wounds, including the genitalia and anus (where bloodstream absorption is enhanced). The genital and anal areas will be protected by placing a clean diaper on the study subject prior to initiation of CHG bath. Cleansing of the feet/heels with CHG will be avoided due to the possibility of blood sample contamination as explained by Cowen et al (1979). Nurses will document completion of the CHG baths on the CHG Bath Data Collection Tool that will be kept at each participant's bedside. When a bath needs to be delayed for clinical reasons, it will be done as close to the scheduled time as possible.

Cleansing between CHG baths: Cleansing of infants between CHG baths may be required if they become soiled. These baths or partial baths will be done per NICU standard of care using (non-CHG) Comfort Cloths by Sage Products Inc. and documented on the CHG Exposure and Comfort Cloth Bath Log (Appendix C).

CHG Exposure: Infant participants have the potential for additional CHG exposures for central line insertions, dressing changes, and perioperative bathing. Additional CHG exposures will be recorded on the CHG Exposure and Comfort Cloth Bath Log.

Monitoring for Adverse Events

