Does twice weekly CHG baths lead to rising (cumulative) CHG blood levels, liver function tests (LFTs -AST/ALT) and Serum Creatinine over time in a sample of infants 36 weeks PMA or older, and less than 2 months of age (48 weeks PMA) with a CVC?

Data Analysis 2:

Descriptive statistics including mean, median, range and frequencies will be used to describe CHG, LFTs and serum Creatinine blood levels over time. We will examine scatterplots and other graphical analysis of blood level dispersion over time to look for relationships.

Sample Size Justification. The primary quantitative goal of this study is estimation of the adverse event rate per 100 patient days. The study sample size will impact the precision of this estimate, and we will establish an upper bound on the rate if zero adverse events occur. In this context, we designed the study sample to expand the existing knowledge base.

Based on recent safety data (Quach, et al 2014) on roughly 200 neonates which recorded no adverse events, we assume the rate of adverse events using CHG bath is lower than 5 events per 1000 days of post-exposure follow-up. We propose following N=50 subjects over 7 days of post-exposure follow-up, for a total of 350 observation days. Assuming rates of 3.5 events or 1.0 events per 1000 days of follow-up, the probability that at least one subject will experience an adverse event is roughly 83% or 40% respectively. Using Monte Carlo simulations, the mean upper bound for estimable rates is 5.5 events per 1000 days.

Auditing and Inspecting:

The sponsor-investigator will permit study-related monitoring, audits, and inspections by the Boston Children's Hospital IRB, the independent data monitor and government regulatory bodies, of all study related documents (e.g. source documents, regulatory documents, data collection instruments, study data etc.). The Investigator will ensure the capability for inspections of applicable study-related facilities.

Human Subjects:

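### CHG from line insertion, dressing changes and perioperative bathing is logged, but Data Analysis 2 makes no use of the log, so a rise (or no rise) in CHG levels cannot be attributed to the study baths

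*Combined protocol and SAP*

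**What the plan says.** All references are to the combined protocol and SAP.

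- **CHG Exposure** (Study Procedures): "Infant participants have the potential for additional CHG exposures for central line insertions, dressing changes, and perioperative bathing". The next sentence reads: "Additional CHG exposures will be recorded on the CHG Exposure and Comfort Cloth Bath Log".
- **Inclusion criteria**: each infant must have "Existing or soon to be placed, peripheral or surgical CVC". Neither the inclusion nor the exclusion criteria mention earlier CHG exposure or a washout.
- **Purpose Statement**: the hospital's ICUs are already "using CHG on a limited basis for CVC insertion and CVC dressing changes on all babies greater than 28 weeks PMA". Enrolment starts at 36 weeks PMA, so this practice covers every participant.
- **Setting**: in the CICU, "nearly 100% of infants requiring surgical correction for their cardiac anomaly have at least 1 CVC placed".
- **Hypothesis 2**: twice-weekly baths do not produce cumulative CHG levels.
- **Procedures for Obtaining CHG, ALT, AST and HCT levels**: one CHG level at baseline, then one each Friday. Study baths fall on Mondays and Thursdays.
- **Data Analysis 2**: "Descriptive statistics including mean, median, range and frequencies will be used to describe CHG, LFTs and serum Creatinine blood levels over time". Scatterplots and other graphs of levels over time are added. No exposure variable and no change from baseline is named.
- **Phototherapy**: this factor is recorded so that its relation to CHG level can be examined. No such use is stated for non-study CHG.

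**The concern.** Hypothesis 2 is about the cause of any change in CHG level: it concerns what the baths do. In an infant with a CVC, the level drawn on a Friday reflects study baths plus whatever CHG was used for the line, its dressing or an operation. With one arm, no unbathed group shows the contribution of routine care. Only the exposure record can help separate the sources, and the stated analysis does not call on it.

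The error has no fixed direction. Line insertion shortly before the baseline draw can lift the starting level and hide a later rise. Insertion or perioperative CHG after baseline can produce a rise that the baths did not cause. The entry criterion admits both kinds of infant.

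The levels are also meant to help determine safe blood levels (CHG blood levels section), and the pilot is meant to support a larger study (Purpose Statement). A mistaken reading of accumulation would carry forward into both.

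**Working it through.** The plan states no figure on this point, so there is none to reproduce. The check has two parts.

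**1. Where the exposure log appears.** The log is named only under Study Procedures (cleansing between baths, and CHG Exposure). It is not named in the online database contents under Data Collection, in the planned associations between CHG level and adverse reactions, in Data Analysis 1 or 2, or in the summary sent to the data and safety monitoring committee (DSMC). The plan therefore provides for recording the exposure but states no analytic use of it.

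**2. Can a plot of level against time separate the sources?** This is an illustration only. The documents give no half-life for CHG and no frequency or amount of non-study CHG, so these are assumptions, shown over a range.

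Inputs from the documents: baths on Monday and Thursday (days 0 and 3 of each week), sampling on Friday (day 4). Assumed: first-order decay with half-life *h* days, each bath adding 1 unit, and one extra exposure worth *a* of a bath on a single Thursday.

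Level at time *t* = sum over exposures of amount × 2^(−(*t* − time of exposure)/*h*).

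Worked case, *h* = 1:
- Week-1 Friday, baths only: 2^−4 + 2^−1 = 0.0625 + 0.5 = 0.5625.
- Week-4 Friday (day 25), baths only, all eight baths: 0.5669. Ratio of week 4 to week 1 = 0.5669/0.5625 = 1.01.
- Extra exposure on the Thursday of week 4, *a* = 1: (0.5669 + 0.5)/0.5625 = 1.90. With *a* = 0.1: (0.5669 + 0.05)/0.5625 = 1.10.
- Extra exposure on the Thursday of week 1 instead, *a* = 1: 0.5669/(0.5625 + 0.5) = 0.53. With *a* = 0.1: 0.5669/(0.5625 + 0.05) = 0.93. The carry-over of this exposure to week 4 is 2^−22 or less and is ignored here.

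The same calculation at other half-lives, with carry-over included, gives these week-4 to week-1 ratios:

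| Assumed half-life (days) | Baths only | Extra in week 4, *a* = 0.1 to 1 | Extra in week 1, *a* = 0.1 to 1 |
|---|---|---|---|
| 0.5 | 1.00 | 1.10 to 1.99 | 0.91 to 0.50 |
| 1 | 1.01 | 1.10 to 1.90 | 0.93 to 0.53 |
| 2 | 1.10 | 1.17 to 1.84 | 1.02 to 0.63 |
| 4 | 1.41 | 1.48 to 2.04 | 1.33 to 0.88 |

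Two readings matter. At a half-life of 1 day or less the baths alone produce essentially no rise, yet one late extra exposure produces an apparent one. At 4 days the baths alone produce a 41% rise, yet one early extra exposure equal to a bath turns it into an apparent fall (0.88). A plot against time cannot tell these cases apart. Placing the extra exposure the day before sampling makes the effect large; an earlier exposure would leave less.

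**The case against.** The strongest reply is that this is a descriptive pilot, that serum CHG is expressly not the primary method of determining adverse reactions, and that the sponsor foresaw the issue and created a log for it. Looking for relationships graphically does not bar the team from consulting the log. The population is infants with a CVC, for whom CHG line care is already practice, so finding no rise despite extra exposure would usually be reassuring. Much of this stands and limits the weight of the point. It does not remove it: Hypothesis 2 concerns the baths, no use of the log is planned, and an elevated baseline is the case in which no rise is not reassuring.

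Several stronger readings are tempting, and the documents do not support them.

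- *That every infant receives non-study CHG.* The text speaks of potential exposure. The entry criterion and unit practice make it likely for most; they do not establish it for all.
- *That non-study CHG will be reported as absorption from the baths.* The plan does not say so. The gap is that the stated analysis gives no means of avoiding it.
- *That exposure before enrolment goes unrecorded, or that the log stays outside the database.* The log form (Appendix C) is not shown, so its fields are unknown. Data Management and Quality Control says that data go on case report forms and from there into the database. A baseline CHG level is also drawn, and could help with earlier exposure if it were used; it cannot separate exposures during the study.
- *That a perioperative bath raises weekly exposure by half (2 to 3), or makes up a third of an infant's total.* The documents give neither the extent nor the frequency of perioperative bathing. The holding rules for clinical instability suspend study baths in the immediate post-operative period, which makes three baths in a surgical week less likely. The one-third figure also rests on the 7-day follow-up in the sample-size section, whereas bathing can run for 12 weeks.

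**Conclusion.** The point holds as a gap in Data Analysis 2. Followed as written, the analysis cannot attribute a rise in CHG level, or its absence, to the twice-weekly baths. The bias can go in either direction. Its size cannot be computed from the documents, and the ratios above show only that it could reverse the reading under plausible assumptions.

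The conclusion rests on three things in the text: likely non-study exposure in an all-CVC sample, a single arm, and an analysis by time alone. It does not rest on any assumed half-life.

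A reader might extend the point to the primary safety result. That is not supported to the same degree: safety is judged by visual and clinical assessment, and the primary outcome counts any adverse event without regard to cause. This is an inexpensive improvement worth making, and no ground for doubting the study as a whole.

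**What to change.** **Data Analysis 2.** Flag every CHG level by the type and date of any non-study CHG exposure logged since the previous level. For the baseline level, use any exposure shown in the chart for the preceding 7 days. Keep all levels as the main display, with flagged levels marked. Add two sensitivity displays: one that excludes levels with any flagged exposure, dressing changes included, and one that excludes only those with insertion or perioperative exposure.

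**Data Analysis 1.** Annotate the adverse-event listing with any non-study CHG exposure in the preceding 7 days. Do not split the event rate by exposure. At the plan's assumed rates, 350 days give 350 × 1.0/1000 = 0.35 to 350 × 3.5/1000 = 1.2 expected events, too few to divide.

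**Leave the baseline draw where it is.** Moving it to after line insertion would let insertion CHG raise the baseline and hide a later rise in those infants.

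**Cost.** A few sentences of analysis text and a short chart look-back, with no extra blood drawn. The restricted displays will hold fewer levels and may over-represent less sick infants. Excluding a flagged level also does not remove carry-over into the next one. These are reasons to keep the all-levels display as the main one.

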Assessment of Liver and Renal Function. Most drugs or chemicals are excreted from the body via the hepatic or renal systems. Therefore, standard LFTs, namely AST and ALT, and the Serum Creatinine levels will be monitored on all subjects. If these labs have been obtained as part of the standard of care, the results will be used by the study team and not repeated in order to minimize additional blood loss or iatrogenic anemia. However, if the study subject's diagnosis did not warrant monitoring of these labs, they will be obtained weekly with the CHG blood level.

Procedures for Obtaining CHG, ALT, AST and HCT levels. A single CHG level will be obtained at baseline and then weekly on Fridays for the remainder of the study for each study participant. Every Friday additional labs will be obtained to monitor liver and renal function (AST, ALT, Serum Creatinine) and HCT for anemia.

Often these lab values are obtained as part of routine care in the ICU. If these labs have not been obtained, they will be added to the weekly labs that will require an additional 1.0 mLs. The study personnel performing the bath will assess the need for the additional labs and notify the bedside nurse so that these labs can be obtained at the appropriate time as per the CHG Study Research Order (Appendix F). The study labs will be drawn with other lab work via central line whenever possible. If no other lab work is scheduled to be obtained, or if the central line gauge is too small (less than 2.6 Fr), then the labs will be obtained at the designated time by heel stick. When no other lab work is to be obtained, infants will need 1-2 heel sticks per week for a required sample of 1- 1.5 mLs in order to limit access of CVC and minimize risk of infection. Standard heel sticks are safely performed on patient care units using the lateral aspect of the infants' pre-warmed heel. Blood levels will be recorded on the CHG Lab Work Log (Appendix G) and entered into a computerized database. Lab specimens for this study will be tracked by utilizing a CHG Study Lab Requisition Form (Appendix H) that bears the patients study ID number followed by a unique specimen identifier (i.e. Patient ID "#CHG001" followed by unique lab identifier "3456").

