Phototherapy. To track study participants who are receiving phototherapy we will include a data collection point on the CHG Skin Assessment Log. This data collection point will enable the RN completing every 12 hours skin assessments to indicate if the infant is receiving phototherapy. This will allow the investigators to determine if a relationship between CHG level and phototherapy exists.

Study Participation Ends. Infants will remain in the study up to 48 weeks PMA (maximum of 12 weeks), upon hospital discharge/transfer, or until the CVC is removed.

Data Management and Quality Control. The Cardiovascular and Critical Care Nursing Research Group (CCNRRG) will be responsible for all data management procedures and will provide support to the research team during the course of the investigation. The CCNRRG employs experienced research personnel. Also all study staff will be CITI program trained. Study staff will have access to designated desk spaces and hospital maintained computer and printing systems.

Standard procedures to ensure accurate and reliable collection of data will include well designed forms with clear instructions, training of staff, and on-going monitoring of all study activities. A manual of operations that describes the purpose of the study, eligibility criteria, and all intervention and assessment procedures will be developed by the study investigators. Study staff will be trained by the study investigators to conduct informed consent, bathing technique, research assessments, and complete case report forms. Furthermore, the primary investigator will provide oversight of all research activities to ensure proper data collection procedures and to monitor staff performance.

Subject confidentiality will be maintained using unique study identification codes. The CHG Active Study Participant Log (Appendix J) will be used to assign ID numbers and to record the identifiers for contacting and tracking subjects. An electronic copy of the log will be kept by the data manager in a file accessible only to study staff, in a computer folder with restricted access. Identifiable data, such as patient name, contact information and medical record numbers will be recorded and stored separately from the research data.

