BCH Committee for Clinical Investigation approval will be obtained before study procedures commence. All study staff will be Citi-program trained. Informed consent/HIPPA forms will be secured before initiation of any study procedures. A computerized database to track subjects through the research continuum will be developed and housed on a password-protected site behind the BCH firewall. Subjects will be assigned study ID numbers that will appear on all study materials and that will be utilized in place of subjects' names in the computerized database. A separate (electronic) CHG Study ID Assignment Log linking subject's names and ID numbers will be maintained by study personnel and kept in a locked cabinet behind a locked door. Only approved study personnel will have access to the log.

This study is considered greater than minimal risk with a potential for direct benefit. There is strong evidence that CHG will help prevent HAIs, however the safety profile for using CHG in infants less than 2 months of age (48 weeks PMA) is not known. To monitor for adverse events, the study team has developed a Data Safety Monitoring Plan (DSMP) and adverse event management plan (see Table 1). Adverse events to CHG baths include mild to severe skin lesions and possible absorption of CHG into the blood that could result in more serious problems such as respiratory, renal and liver problems or anaphylaxis. Thus the study team is taking a conservative approach. In an attempt to usurp the benefits associated with CHG while concurrently minimizing the likelihood of adverse events, study subjects will receive twice-weekly, instead of daily, CHG baths.

While these baths still place the subjects at risk for adverse events we believe twice-weekly baths will minimize these risks. To monitor for adverse events the study team has developed the following procedures:

1. Study RNs will perform a full body skin assessment for skin irritation or open areas prior to each bath.
2. Bedside RNs will complete skin assessments every 12 hours during the course of the study.
3. A plan is in place for Management of Adverse Events to the CHG Baths. (Table 1.)
4. To monitor for absorption into the blood, infants will have blood levels (CHG, ALT, AST, and Serum Creatinine) drawn at baseline and weekly and when an infant is removed from the study in response to an adverse event. In addition, infants will be monitored weekly for the development of iatrogenic anemia.

Data Safety Monitoring Plan:

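### No study blood draw is scheduled at routine exit, so many bathed infants may leave without a CHG level after the last bath, and some without any post-bath level

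*Combined protocol and SAP*

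**What the plan says.** All places are in the combined protocol and SAP.

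- **Baths** (CHG Bath Intervention): "Baths will be performed every Monday and Thursday during the day shift".
- **CHG draws:** "A single CHG level will be obtained at baseline and then weekly on Fridays for the remainder of the study for each study participant" (in the section Procedures for Obtaining CHG, ALT, AST and HCT levels).
- **Other labs** (same section): "Every Friday additional labs will be obtained to monitor liver and renal function (AST, ALT, Serum Creatinine) and HCT for anemia".
- **Routine-care results** (Assessment of Liver and Renal Function): "If these labs have been obtained as part of the standard of care, the results will be used by the study team" and are not repeated. The next section adds: "Often these lab values are obtained as part of routine care in the ICU". Neither section says when, relative to a bath, such a result must have been drawn.
- **Routine exit** (Study Participation Ends): apart from the age and 12-week limits, infants leave "upon hospital discharge/transfer, or until the CVC is removed". No draw is attached.
- **Exit draw** (Human Subjects, monitoring procedure 4): CHG, ALT, AST and creatinine are "drawn at baseline and weekly and when an infant is removed from the study in response to an adverse event".
- **Hold-related levels** (Holding and Stopping Rules): two CHG levels within a week of the bath after an adverse-event hold or a clinical-instability hold, waived if the previous level was not detectable.
- **Skin** (Full Body Skin Assessment): the last check is 36 hours after the last bath or before discharge, whichever is first. Blood sampling has no matching rule.

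**The concern.** Research Question 2 asks whether CHG, liver tests and creatinine rise with repeated baths. An infant's bath count is highest after the last bath. An infant who leaves between the Monday bath and the Friday draw has no scheduled sample after that bath. One whose first bath was that Monday or Thursday and who leaves before Friday has no scheduled post-bath sample at all.

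The second consequence is for the primary outcome, the proportion of subjects with any adverse event (Data Analysis). Table 1 makes AST, ALT and creatinine thresholds adverse events. An infant with no such result after a bath cannot show one of these events, yet stays in the denominator as event-free. A routine-care value drawn before that week's baths can also stand in as the week's safety lab.

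**Working it through.** The plan gives no figure for the share of infants with a post-bath sample, so there is nothing to reproduce. The check is calendar arithmetic.

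**Inputs from the documents:** baths Monday and Thursday, scheduled draws on Friday, hours not given; routine exit on any day.

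**Assumptions, not in the documents:** the weekday distribution of exits, the distribution of stay, the share of exits through holds, and how often routine-care labs follow the last bath.

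**1. Last bath unsampled, routine exits, scheduled draws only.** An exit from the Monday bath up to the Friday draw is uncovered. An exit from the Friday draw up to the Monday bath is covered.

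- Uniform exits, bath and draw at the same hour: (72 h + 24 h) / 168 h = 96/168 = 4/7 = 57.1%.
- By whole days: 3/7 = 42.9% if Monday exits precede the bath and Friday exits follow the draw; 5/7 = 71.4% in the opposite case.
- By hour, with a Monday bath between 07 and 19 h and a Friday draw between 00 and 24 h: from (96 + 0 − 19)/168 = 45.8% to (96 + 24 − 7)/168 = 67.3%.
- Exits on weekdays only, 08 to 20 h: 61.7% to 100% over the same bath and draw hours.
- Simulated exponential stays, mean 7 to 15 days, bath and draw at 10 h: 59% to 61% of bathed infants.

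**2. Allowing for holds (CHG).** If a share x of infants exits through holds and all of them get a later level, the uncovered share is (1 − x) × 57.1%.

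| x | Uncovered |
|---|---|
| 0% | 57.1% |
| 10% | 51.4% |
| 12.5% | 50.0% |
| 20% | 45.7% |

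**3. Allowing for routine-care labs (AST, ALT, creatinine).** If a share q of uncovered infants has a routine result after the last bath, the uncovered share is 57.1% × (1 − q).

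| q | Uncovered |
|---|---|
| 12.5% | 50.0% |
| 25% | 42.9% |
| 50% | 28.6% |

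**4. No scheduled post-bath sample at all.**

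- Every infant followed for exactly 7 days from the first bath (the follow-up in Sample Size Justification): a Friday always falls inside, so 0%.
- First baths split equally between Monday and Thursday, exponential stay with mean m days from the first bath: 0.5 × (1 − e^(−4/m)) + 0.5 × (1 − e^(−1/m)).
  - m = 7: 0.5 × 0.435 + 0.5 × 0.133 = 28%
  - m = 12: 0.5 × 0.283 + 0.5 × 0.080 = 18%
  - m = 15: 0.5 × 0.234 + 0.5 × 0.064 = 15%
- The simulation in step 1 gives 25% (mean 7) to 13% (mean 15) of bathed infants with no Friday draw since enrolment. It counts a Friday draw before the first bath as coverage.

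The range is therefore 0% to about 28%, or 0 to about 14 of 50 infants.

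**5. Effect on the lab part of the primary proportion.** If a share u has no post-bath lab and would have had the same risk as the rest, the all-infant lab-event proportion is (1 − u) times that among tested infants: 0.72 at u = 28%, 0.87 at u = 13%, 1 at u = 0. Suitable routine-care values move the factor towards 1.

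**The case against.** The case on the other side is substantial.

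- **Draws are not confined to Fridays.** There is a baseline level, a draw at adverse-event removal, and the hold-related levels. The instability hold covers the immediate post-operative period, which matters in a cardiac ICU. This stands, and it limits the gap to routine exits. The hold levels are not guaranteed, though: read literally, the previous level that waives them could be the pre-bath baseline.
- **A reader might infer that more than half of all infants leave with no CHG, liver or creatinine result after the last bath.** The documents do not support that. The 57% needs uniform exits and applies to routine exits. For CHG it falls to 50% or less once 12.5% exit through holds with extra levels. For liver tests and creatinine it reaches 50% once 12.5% of uncovered infants have a routine result after the last bath, and the plan says such labs are frequent.
- **A reader might also take 14 of 50 as the number with no post-bath lab.** That needs exponential stays with mean 7 days. The 7 days in the sample-size section is a follow-up length, not such a mean, and the stays under Setting describe unit admissions, not time on study with a CVC.
- **Missing CHG levels do not bias the primary proportion.** No CHG level is a Table 1 event. Visual and clinical assessment is the primary safety measure, and the skin check has its own end rule. Only the AST, ALT and creatinine part of this point touches the primary proportion.
- **Friday sampling has a merit.** It follows both weekly baths at a roughly constant one-day lag, so weekly values are comparable. Exit samples would vary in lag and bath count. This stands and shapes the fix.
- **Other safeguards exist.** The DSMC reconsiders lab frequency after 10 subjects, status reports track missing data, and the research order (Appendix F), which is not in the documents, may say more about timing. None of these is shown to supply an exit sample.

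**Conclusion.** The point holds in a limited form. No study draw is tied to CVC removal, discharge or transfer, and nothing requires a substituted routine-care liver or creatinine value to follow a bath.

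For CHG, about 4/7 of routine exits would lack a scheduled level after the last bath if exits are uniform, 43% to 71% by whole days. More would be missed if exits cluster on weekdays. The share with no scheduled post-bath level at all lies between 0% and roughly 28%, and the documents cannot place it more closely. For AST, ALT and creatinine the gap is smaller by an unknown amount.

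The consequences are thinner data for Research Question 2 where bath count is highest, and a downward pull of unknown size on the lab-event part of the primary proportion. The skin findings are unaffected. The change should be made because it is cheap; the point does not invalidate the design.

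**What to change.** 1. In Procedures for Obtaining CHG, ALT, AST and HCT levels and in monitoring procedure 4, add: when a routine exit is planned and no study sample has been drawn since the last bath, take that week's study sample before the line is removed or with the last clinical blood work.
2. Record time since last bath and number of baths for every sample, and show exit samples separately from Friday samples.
3. Count a routine-care AST, ALT or creatinine value as a post-bath result only if it was drawn after a study bath that week.
4. Report how many infants have at least one post-bath lab. Give lab events with that number as denominator, alongside the all-infant proportion.

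**Cost.** Items 1 to 3 need a few protocol sentences, a line on the research order and two data fields; item 4 is analysis only. For an infant leaving before Friday the sample is an added one, since that Friday draw would not have happened. It stays within the 1.5 mL weekly maximum in Assessment for Iatrogenic Anemia. The 12-week total there should be restated: its listed parts give 0.5 + 12 × 1.5 = 18.5 mL (18 is printed), and one exit sample brings this to at most 20.0 mL. A pre-bath routine lab will occasionally have to be repeated, against the plan's aim of sparing blood. Exit samples will have a variable lag after the bath, and unplanned exits will still be missed.
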